2.4.5.2 Analyses of adverse events

Generalities

The primary focus of adverse event reporting will be on treatment-emergent adverse events. Pretreatment and posttreatment adverse events will be described separately.

If an adverse event date/time of onset (occurrence, worsening, or becoming serious) is incomplete, an imputation algorithm will be used to classify the adverse event as pretreatment, treatment-emergent, or posttreatment. The algorithm for imputing date/time of onset will be conservative and will classify an adverse event as treatment emergent unless there is definitive information to determine it is pretreatment or posttreatment. Details on classification of adverse events with missing or partial onset dates are provided in [Section 2.5.3](#).

Adverse event incidence tables will present the number (n) and percentage (%) of patients experiencing an adverse event by SOC, HLG, HLT, and PT, sorted by the internationally agreed order for SOCs and alphabetical order for HLG, HLT and PT within the SOC. Multiple occurrences of the same event in the same patient will be counted only once in the tables within a treatment phase. The denominator for computation of percentages is the safety population within each treatment group.

Sorting within tables ensures the same presentation for the set of all adverse events within the observation period (pretreatment, treatment-emergent, and posttreatment). For that purpose, the table of all treatment-emergent adverse events presented by primary SOC and PT (sorted by the internationally agreed SOC order and decreasing frequency of PTs within SOCs in the sotagliflozin 400 mg group) will define the presentation order for all other similar tables unless otherwise specified. In case of equal frequency regarding PTs, alphabetical order will be used.

Analysis of all treatment-emergent adverse events

The following treatment-emergent adverse event summaries will be generated for the 26-week core treatment period and the 52-week entire treatment period for the safety population.

- Overview of treatment-emergent adverse events, summarizing number (%) of patients with any
 - TEAE,
 - Serious TEAE,
 - TEAE leading to death,
 - TEAE leading to permanent treatment discontinuation.
- All treatment-emergent adverse events by primary SOC, showing number (%) of patients with at least 1 treatment-emergent adverse event, sorted by internationally agreed order of primary SOC.
- All treatment-emergent adverse event by primary SOC, HLG, HLT, and PT, showing number (%) of patients with at least 1 treatment-emergent adverse event sorted by the

SOC internationally agreed order. The other levels (HLGT, HLT, PT) will be presented in alphabetical order.

- Number (%) of patients experiencing TEAE(s) presented by PT, sorted by decreasing incidence of PT in the sotagliflozin 400 mg group.
- All treatment-emergent adverse events by primary SOC and PT, showing the number (%) of patients with at least 1 treatment-emergent adverse event, sorted by the internationally agreed SOC order and by decreasing incidence of PTs within each SOC in the sotagliflozin 400 mg group. This sorting order will be applied to all similar other tables, unless otherwise specified.
- All treatment-emergent adverse events regardless of relationship and related to IMP by primary SOC, HLGT, HLT and PT, showing the number (%) of patients with at least 1 treatment-emergent adverse event, sorted by the internationally agreed SOC order. The other levels (HLGT, HLT, PT) will be presented in alphabetical order.
- All treatment-emergent adverse events by maximal severity, presented by primary SOC and PT, showing the number (%) of patients with at least 1 treatment-emergent adverse event by severity (ie, mild, moderate, or severe), sorted by the sorting order defined above.
- Common TEAEs (PTs with incidence $\geq 2\%$ in any treatment group) by primary SOC, HLGT, HLT and PT, sorted by the internationally agreed SOC order. The other levels (HLGT, HLT, PT) will be presented in alphabetical order.
- Common TEAEs (PTs with incidence $\geq 2\%$ in any treatment group) will be provided as appropriate by primary SOC and PT and by demographic factors including gender, age group (<50, ≥ 50 to <65, ≥ 65 years), race (White, Black or African American, Asian, Other), baseline SBP category (<130, ≥ 130 mmHg), and baseline eGFR category, prior antidiabetic medication (No antidiabetic therapy, Insulin [alone or with other antihyperglycemic agents], SU and/or glinide [alone or with other non-insulin antihyperglycemic agents], Other [non-insulin antihyperglycemic agents except SU and glinide]). SOC will be sorted by the internationally agreed order and the PT by decreasing incidence within each SOC in the sotagliflozin 400 mg group, as described above.
- TEAEs (PTs with incidence $\geq 5\%$ in any treatment group) by primary SOC, HLGT, HLT and PT, sorted by the internationally agreed SOC order. The other levels (HLGT, HLT, PT) will be presented in alphabetical order.
- Acute renal failure (narrow search on “Acute renal failure (SMQ)” [20000003]) by PT.

Analysis of all treatment emergent serious adverse event(s)

- All treatment-emergent serious adverse events by primary SOC, HLGT, HLT, and PT, showing the number (%) of patients with at least 1 serious treatment-emergent adverse event, sorted by the internationally agreed SOC order. The other levels (HLGT, HLT, PT) will be presented in alphabetical order.
- All treatment-emergent serious adverse events regardless of relationship and related to IMP, by primary SOC, HLGT, HLT, and PT, showing the number (%) of patients with at

least 1 treatment-emergent serious adverse event, sorted by the internationally agreed SOC order. The other levels (HLGT, HLT, PT) will be presented in alphabetical order.

Analysis of all treatment-emergent adverse event(s) leading to treatment discontinuation

- All treatment-emergent adverse events leading to treatment discontinuation, by primary SOC, HLGT, HLT, and PT, showing the number (%) of patients sorted by the internationally agreed SOC order. The other levels (HLGT, HLT, PT) will be presented in alphabetical order.

Analysis of adverse events of special interest

The summaries of AESI will be presented for the 52-week entire treatment period only in the safety population.

Pregnancy and overdose will be included in overall AE summaries if any are reported. ALT increase >3 x ULN is included in laboratory PCSA summary if any.

In addition, the number (%) of patients with an AESI will be summarized by PT and by treatment group. Corresponding listings will be provided as appropriately.

Analysis of events of special interest

The summaries of EOSI will be presented for the 52-week entire treatment period only in the safety population.

CV events, bone fracture and DKA

For EOSIs that are adjudicated (ie, deaths, myocardial infarction, stroke, and unstable angina requiring hospitalization, heart failure requiring hospitalization, bone fracture, and diabetic ketoacidosis), the number (%) of patients with an EOSI positively adjudicated by CEC will be summarized by treatment group. All EOSIs sent for adjudication and/or reported by the Investigators in the specific AE forms will be listed along with the adjudication outcome.

Renal events

For the EOSI renal events where selected events are adjudicated, the number (%) of patients with any renal events identified in [Table 3](#) in [Section 2.1.4.2](#) will be summarized by treatment group.

The following renal events will be listed along with the adjudication outcome if applicable, including events,

1. Recorded in eCRF “GFR decrease”.
2. Recorded in eCRF “Renal Event - Dialysis”.
3. Identified as “Renal transplant” in eCRF “Other procedure”.

Renal death will be part of all deaths specified above.

Other EOSIs

For EOSIs that are not adjudicated, the number (%) of patients with at least one event will be summarized by treatment group and by PT (as identified in [Table 3](#) in [Section 2.1.4.2](#)).

Severe hypoglycemia will be included in the summary of hypoglycemia (See [Section 2.4.5.1](#)).

AE leading to an amputation is described in the section below.

Analysis of Amputation

The number (%) of patients with amputation will be summarized by treatment group and by PT and LLT during the study (ie, regardless of on- or post-treatment). Amputation is a procedure recorded in eCRF “Other Procedures related to Amputation”. Patients who had a procedure related to amputation will be listed.

The number (%) of patients with an “AE leading to an amputation” will be summarized by treatment group and by PT. The “AE leading to an amputation” is determined by the AE identifier recorded in eCRF “Other Procedures related to Amputation” when “AE correction” is chosen as the reason for the amputation procedure.

In addition, the number (%) of patients with an “AE potentially leading to an amputation” will be summarized by treatment group and by PT (as identified in [Table 3](#) in [Section 2.1.4.2](#)); these PTs in [Table 3](#) were requested by the European Medicines Agency/Pharmacovigilance Risk Assessment Committee [EMA/PRAC] Assessment Report 9 February 2017). The associated list will be provided as well, with patients who had an amputation procedure flagged. “AE potentially leading to an amputation” represents the condition that may potentially lead to the amputation procedure, but not in all cases an amputation has occurred (as per the EMA/PRAC request).

Analysis of pretreatment and posttreatment adverse events

- All pretreatment adverse events by primary SOC and PT, showing the number (%) of patients with at least 1 pretreatment adverse event, sorted by the internationally agreed SOC order and decreasing incidence of PTs within each SOC in sotagliflozin 400 mg group
- All posttreatment adverse events by primary SOC and PT, showing the number (%) of patients with at least 1 posttreatment adverse event, sorted by the internationally agreed SOC order and decreasing incidence of PTs within each SOC in sotagliflozin 400 mg group

Listings

Supportive AE listings will be provided for all AEs, SAEs, and deaths, AEs leading to treatment discontinuation and/or death, and EOSI as appropriate. Listing of all AEs, SAEs and AEs leading to treatment discontinuation and/or death, sorted by treatment, patient identification, and onset date will include the following information: treatment, patient identification, country, age, gender, race, BMI, primary SOC, PT, reported term, onset date, study day (relative day to the start date of

double-blind treatment), AE duration, duration of exposure, intensity, corrective treatment, action taken with IMP, date of treatment discontinuation (if relevant), relationship to IMP or NIMP, outcome, date of death (if any), seriousness, seriousness criteria, and AE status (“E” for TEAE; and “P” for on-study post-treatment AE).

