SGLT2 inhibitors class have been associated with small decreases of glomerular filtration rate and increased rate of genital infections, which are usually mild and well tolerated in clinical trials. Overall, sotagliflozin has been well-tolerated in all studies to date, with the majority of events assessed as mild to moderate; most of which resolved spontaneously. Serious AEs and discontinuations due to AEs have been limited and balanced between treatment and comparator groups.

Events of special interest (EOSI) are evaluated based on either their potential link to the drug's mechanism of action, events that occur in other SGLT-inhibitor drugs, or regulatory interest/guidance for diabetes products, but found not to be in imbalance in clinical trials. In addition to the identified and potential risks (genital mycotic infections [male and female], metabolic acidosis, DKA, urinary tract infections [UTIs], volume depletion, severe hypoglycemia) for the sotagliflozin program, other EOSI have been defined. These EOSI are: major adverse cardiac events (MACEs) and other CV events, venous thrombotic events (VTEs), drug-induced liver injuries (DILIs)/alanine aminotransferase (ALT) increase  $>3$  times the upper limit of normal (ULN), diarrhea, pancreatitis, bone fractures, renal events, malignancies of special interest (including but not limited to: breast, bladder, renal cell, Leydig cell, pancreatic, prostate and thyroid cancer), and AEs leading to amputation.

However, reports of these events have been infrequent and have responded to standard treatment. The improvement in glycemic control, the reductions in weight and BP, and the tolerability and safety profile of sotagliflozin to date, demonstrate a favorable benefit-risk assessment for sotagliflozin.

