2.1.4.2 Adverse events variables

Adverse event observation period

- Pretreatment adverse events are adverse events that developed or worsened or became serious from the signed informed consent date up to first administration of double-blind IMP.
- Treatment-emergent adverse events are adverse events that developed or worsened or became serious during the treatment-emergent adverse event period.
- Posttreatment adverse events are adverse events that developed or worsened or became serious during the posttreatment period.

All adverse events (including SAE, AESI and EOSI) will be coded to a LLT, PT, HLT, HLG, and associated SOC using the version of MedDRA currently in effect at Covance at the time of database lock.

The occurrence of adverse events (including SAE, AESI and EOSI) will be recorded from the time of signed informed consent until the end of the study (see [Section 2.1.4](#)) or the resolution/stabilization of all SAE, AESI and EOSI.

AESI include:

- Pregnancy.
- Symptomatic overdose with IMP/NIMP.
- Alanine aminotransferase (ALT) increase >3 times upper limit of normal (ULN).

EOSI include:

- MACE (CV death, MI, or stroke) and other specific CV events (eg, heart failure requiring hospitalization).
- Severe hypoglycemia (see [Section 2.1.4.1](#)).
- Genital mycotic infections (to include vulvovaginal candidiasis in females and candida balanitis in males).
- Urinary tract infections.
- Clinically relevant volume depletion and events related/possibly related to volume depletion.
- Diarrhea.
- Pancreatitis.
- Bone fractures.
- Venous thrombotic events, to include deep venous thrombosis and thromboembolism (to include pulmonary embolism).
- Diabetic ketoacidosis (DKA).

- Renal events, to include 50% decline in eGFR, end-stage kidney disease, renal death.
- Malignancies of special interest (breast, bladder, renal cell, Leydig cell, pancreatic, prostate, and thyroid cancer).
- AE leading to an amputation.

The Clinical Endpoint Committee (CEC) will, in a blinded manner review and adjudicate all deaths, myocardial infarction, stroke, unstable angina requiring hospitalization, and heart failure requiring hospitalization, selected renal events, bone fracture, and DKA.

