Sustained eGFR <15 mL/min/1.73 m ²	(2) For eGFR <15 mL/min/1.73 m ² , (2a) confirmed eGFR <15 mL/min/1.73 m ² for ≥30 days with no reversible cause as recorded in eCRF "eGFR decrease", OR (2b) positively adjudicated by CEC: Yes to the question "Does the subject meet the criteria of CKD progression".
Chronic dialysis	(3) For dialysis, (3a) dialysis lasted for ≥90 days (eg, end date - start date+ 1 ≥90) as recorded in eCRF "Renal Event - Dialysis", OR (3b) positively adjudicated by CEC: Yes to the question ". Does the subject meet the criteria for ESRD".
Renal transplant ^a	(4) "Renal transplant" captured in eCRF "Other procedure form", where adjudication is not required. PTs of Renal transplant (10038533), Renal and pancreas transplant (10052278), Renal and liver transplant (10052279) based on MedDRA v21.1.
Renal death	(5) Renal death as positively adjudicated by CEC: "Death - Non-Cardiovascular (Renal)" as the primary cause of death
EOSI not adjudicated^a	
Severe hypoglycemia	Algorithm specified in Section 2.1.4.1 based on eCRF "Hypoglycemic Events"
Genital mycotic infections	PTs in Appendix C
Urinary tract infections	PTs in Appendix C
Clinically relevant volume depletion and events related/possibly related to volume depletion	PTs in Appendix C
Diarrhea	Narrow search on "Noninfectious diarrhoea (SMQ)" [20000218] plus the following PTs (MedDRA v21.1): Gastroenteritis (10017888), Antidiarrhoeal supportive care (10055660), Enteritis (10014866), Enteritis leukopenic (10014877), Enterocolitis (10014893), Enterocolitis haemorrhagic (10014896)
Pancreatitis	PTs in Appendix C
Venous thrombotic events	PTs in Appendix C
Malignancies of special interest	Breast cancer: Narrow search on "Breast neoplasms, malignant and unspecified (SMQ)" [20000149] Prostate cancer: Narrow search on "Prostate neoplasms, malignant and unspecified (SMQ)" [20000152] Leydig-cell cancer: PTs of Leydig cell tumour of the testis (10024407) and Ovarian Sertoli-Leydig cell tumour (10073270) based on MedDRA v21.1 Thyroid cancer: PTs in Appendix C Renal cell cancer: PTs in Appendix C Pancreatic cancer: PTs in Appendix C Bladder cancer: PTs in Appendix C
EOSI AE leading to an amputation	
AE leading to an amputation	"AE Correction" as the reason for amputation in eCRF "Other Procedures related to amputation"
AE potentially leading to an amputation ^{a,b}	PTs in Appendix C

AE Grouping	Criteria

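### SAP 2.4.5.2 sets no same-sex denominator for event terms that only one sex can have, so their absolute incidences shrink with the sex share, and a genital-infection risk by sex is not assured

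*SAP*

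**What the plan says.** The general rule for adverse event tables in SAP 2.4.5.2 is "The denominator for computation of percentages is the safety population within each treatment group". Protocol 11.4.3.1 states the same rule. For events of special interest (EOSI), SAP 2.4.5.2 adds "The summaries of EOSI will be presented for the 52-week entire treatment period only in the safety population" and, for those that are not adjudicated, "For EOSIs that are not adjudicated, the number (%) of patients with at least one event will be summarized by treatment group and by PT". Neither document sets a different denominator for terms confined to one sex.

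Such terms are among the EOSI. SAP 2.1.4.2 lists "Genital mycotic infections (to include vulvovaginal candidiasis in females and candida balanitis in males" as one EOSI, and SAP Table 3 has an entry "Prostate cancer: Narrow search on" the relevant standard query, as well as Leydig-cell terms for testis and ovary. Protocol 4.5 says that the SGLT2 inhibitor class has been associated with an "increased rate of genital infections, which are usually mild and well tolerated in clinical trials", and it counts genital mycotic infection in both sexes among the identified and potential risks.

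The SAP does plan some tables by gender. In 2.4.5.2, common treatment-emergent events (preferred terms at 2% or more in any arm) "will be provided as appropriate by primary SOC and PT and by demographic factors including gender". In 2.4.5.1, severe or documented symptomatic hypoglycemia is also planned by gender. The common rules in 2.4.5 mention selected safety analyses by gender, but refer to 2.4.5.1 and 2.4.5.2 for the detail. They also allow relative risks against placebo with 95% confidence intervals, as an option.

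**The concern.** When a term can occur in only one sex, patients of the other sex add to the denominator and can never add to the numerator. The percentage then mixes the risk of the event with the sex mix of the arm, and tells neither a woman nor a man what her or his own risk is. That matters most for genital infection: the protocol names it as a risk, and Appendix B of the protocol gives separate hygiene advice to women and to uncircumcised men.

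Absolute percentages by arm are the one display that the plan guarantees, so a reader of the report would take the size of the risk from them. Randomization is stratified by HbA1c, SBP and CKD stage (SAP 1.1), not by sex, so a chance difference in sex mix also feeds into a crude comparison of a sex-specific term.

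**Working it through.** **Inputs from the documents.** Planned patients per arm: 780 / 3 = 260, as SAP 1.1 states. This is taken as the approximate safety population of an arm. Cut for the gender table: 2% of an arm. Terms in the genital mycotic infection EOSI (SAP Appendix C): eight. Five are sex-specific (vulvovaginal candidiasis, vulvovaginal mycotic infection, candida cervicitis, balanitis candida, fungal balanitis). Three are not (genital candidiasis, genital infection fungal, urogenital infection fungal).

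**Inputs that are assumed.** The documents give neither the sex mix nor any incidence. The share *s* of the sex at risk is therefore varied, and the incidences below are illustrations.

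**Step 1: dilution of a sex-specific term.** Displayed risk = *s* × same-sex risk. With equal *s* in both arms, displayed difference = *s* × same-sex difference. For 8% versus 1% in women (7.0 points):

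| Share of women | Displayed risks | Displayed difference | Relative risk |
|---|---|---|---|
| 40% | 3.2% v 0.4% | 2.8 points | 8.0 |
| 50% | 4.0% v 0.5% | 3.5 points | 8.0 |
| 60% | 4.8% v 0.6% | 4.2 points | 8.0 |

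The absolute difference shrinks and the relative risk does not.

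**Step 2: strength of the comparison.** Take 10% versus 2% in the sex at risk and *s* = 0.50, so 130 of that sex per arm.
- Same-sex denominator: z = 0.08 / √[(0.10×0.90 + 0.02×0.98)/130] = 2.76.
- All patients: z = 0.04 / √[(0.05×0.95 + 0.01×0.99)/260] = 2.69.

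The two are practically equal.

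**Step 3: chance imbalance in sex.** At *s* = 0.50 and 260 per arm, the SD of the difference in shares between two arms is √(2×0.5×0.5/260) = 4.4 points. Shares of 0.50 and 0.45 would turn a true relative risk of 5.0 into 5.0 × 0.50/0.45 = 5.6, or into 4.5 if reversed.

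**Step 4: what the gender table catches.** The cut is measured over both sexes: 0.02 × 260 = 5.2, so 6 patients with the same term are needed. Six patients are 6/78 = 7.7% of the sex at risk at *s* = 0.30, 6/130 = 4.6% at 0.50, and 6/182 = 3.3% at 0.70. The cut also applies term by term. Suppose that five women in an arm of 130 women are coded to each of four terms (vulvovaginal candidiasis, vulvovaginal mycotic infection, genital candidiasis, genital infection fungal), one term per woman, with no cases in men. Then 20/130 = 15.4% of the women have an event, yet each term stands at 5/260 = 1.9%. If no other arm reaches 2%, no genital-infection row by gender appears. The pooled EOSI row would show 20/260 = 7.7%, without a split by sex.

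**The case against.** The strongest case on the other side is that this is a presentation choice in a descriptive table. No safety test depends on it, whole-arm denominators are the stated rule in both documents, and Step 2 shows that the comparison loses almost nothing. All of that stands.

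The gender table would also catch many realistic cases. If the 8% in Step 1 were coded to a single term, the displayed 3.2% to 4.8% would pass the 2% cut. Split evenly over two terms at a 50% share, it would be 2.0% each, right at the cut. Over three terms it would be 1.3% each and would miss it. Cover therefore depends on how events are coded, and the table is in any case planned only where judged appropriate.

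Same-sex incidences could also be worked out afterwards, because counts are given by arm and term, gender is tabulated by arm, and the listings carry gender. For a reader of the report this is only approximate, since SAP 2.4.1 tabulates demographics in the randomized population. It also fails at the level of the EOSI, where the sex-neutral terms cannot be allocated without the listings.

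A reader might infer more than the documents support:
- **That risks are shown at about half their size.** This is true only for a 50% share, and no sex mix is stated.
- **That the genital mycotic infection total is wrong.** It pools infections of both sexes, so all patients are its proper denominator.
- **That the SAP breaks no EOSI down by sex.** Severe hypoglycemia is an EOSI and is planned by gender.
- **That prostate cancer is a class risk.** Protocol 4.5 ties genital infections and small falls in filtration rate to the class, not prostate cancer, which is only a listed malignancy of special interest.

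**Conclusion.** The point holds in a limited form. For terms confined to one sex, the planned tables scale absolute incidence and absolute arm difference by the sex share, and no text assures a genital-infection risk by sex at EOSI level. The factor is the share itself: 0.4 to 0.6 over the assumed range, which turns an assumed 7.0 points into 2.8 to 4.2. With similar shares across arms the relative risk is unchanged, and a chance imbalance of 5 points moves it by only about a tenth. Inference is not biased and type I error is not affected. What is lost is an interpretable absolute risk for women and for men, for an event that the protocol names as a risk. For prostate and Leydig-cell tumours the same arithmetic applies, but cases may be few and the practical gain is small. This is a cheap improvement worth making, not a flaw that threatens a conclusion.

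**What to change.** Keep the pooled EOSI row and add to SAP 2.4.5.2:

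> Genital mycotic infections (EOSI group and its preferred terms) will also be summarized separately for women and men, with the women or men in the safety population of each treatment group as denominator, regardless of the 2% cut. Other sex-specific EOSI terms (eg, prostate cancer, Leydig cell tumour of the testis, ovarian Sertoli-Leydig cell tumour) will use the same-sex denominator.

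Gender is already collected (SAP 2.1.1) and already appears in the adverse event listings, so no new data are needed. The cost is one paragraph of SAP text and a few extra rows in a descriptive table. The downside is that the by-sex rows rest on smaller denominators and are less precise.
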